Only the research team will have access to individually identifiable private information about human subjects, for the purpose of tracking recruitment and retention, as well as participation payments. All data will be deidentified in study databases. To safeguard confidentiality and anonymity, all data collection instruments will identify participants only by study ID number. Logs linking information to study numbers will be kept locked in a file cabinet in the Project Manager's office. Data analysis staff will not have access to identifying information. We will inform participants of the areas to be covered in the surveys and focus groups prior to their administration. Study participants will be told that if they experience any discomfort while participating in the data collection procedures they can ask to be removed from the study. Also, participants will be told that they do not have to respond to any questions that make them feel uncomfortable. Individuals will be told that their refusal to answer any question will not jeopardize their relationship with their HV program (female clients), their partner's relationship with their HV program (male clients), or their HV colleagues (home visiting supervisors and staff).

Consent forms for female HV clients and their male partners will include a statement that the privacy of family members will be respected and information not shared with anyone else, with the exception of concerns about risk of harm (e.g., suspected child abuse or suicidality). All staff will be certified in online State of Illinois mandated reporter training provided by the Illinois Department of Child and Family Services. Families will be explicitly informed during the consent process that they will be informed if confidentiality must be broken due to mandatory reporting guidelines designed to keep children and families safe. Participants will be invited to be present should the mandated reporting occur.

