Mental health referrals and mandated reporting. There are several types of concerns that may arise that will require review and possible referral: (1) imminent risk of harm and/or potential abuse; (2) observed or reported extreme distress by the parent and/or by the parent in relation to the child; and (3) non-reportable concerns about practices during pregnancy that could be harmful to the fetus. All potential concerns will be overseen by the PI, [name]. We will use procedures developed by the PI to respond to concerns about imminent harm and/or potential abuse. It is possible that some study participants will discuss suicidal ideation or having a suicide plan while discussing MB content. In these cases, home visitors will be directed to call their program supervisor for consultation, or, in extreme cases, 911. Home visitors will remain with participants until an action plan is implemented. While it is unlikely, some study participants may text home visitors with thoughts of harming oneself or another individual. In these cases, home visitors will similarly contact their program supervisor or 911. Home visitors will also be instructed to remain in electronic contact with the study participant. We believe the most likely imminent risk will be study participants who endorse suicidal ideation on research assessments. In these cases, the protocol will be to refer the study participant to a licensed clinical social worker at each HV program (typically the program manager), who will make a determination regarding whether the study participant is in danger of harming herself and will determine necessary steps to ensure the safety of the study participant. In addition, the study team will provide the participant with contact information (telephone and text) for 24-hour suicide and mental health crisis hotlines. Non-imminent concerns will be flagged and discussed in weekly team meetings and shared with providers as necessary. Since survey instruments will be asking about sensitive subjects such as family relationships, life stress, and mental health, it is possible that participants may become distressed. We will train all research staff how to identify distress during assessment procedures, identify flagged items indicating imminent risk (e.g., suicidality), as well as safety protocols to follow in different scenarios.

Phase 1 and 2 of this study will be registered as separate studies on ClinicalTrials.gov.

11.0 Potential Benefits to Participants:

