Data and Safety Monitoring Plan and Board. In the collection of information about depressive symptoms, the research team has the ethical responsibility to appropriately respond to clinical information obtained in this study. Oversight of the data and safety monitoring plan will be the responsibility of the PI, [name], with support from Co-Investigator [name] for data monitoring. [name] has conducted multiple trials of the MB Course with perinatal women in a variety of community settings. [name] has extensive experience as lead biostatistician in numerous behavioral health research projects over the past decade, including those focusing on depression and perinatal populations.

Online Survey:

Any study participant who endorses thoughts of self-harm will be referred to the supervisor at the home visiting program, by the Project Manager. The supervisor, who is trained in responding to and addressing suicidal ideation, will use their agency's protocol to make a determination regarding whether the study participant is in danger of harming herself or others and will determine necessary steps to ensure the safety of the study participant. The Principal Investigator will be notified immediately of any such referrals made by study staff. In addition, should administration of depression scale indicate the participant is experiencing severe depressive symptoms, the supervisor at the home visiting program will be notified in order to provide appropriate referrals for their client's mental health treatment linkage.

During any of the research assessments, if the participant endorses current thoughts of harming herself or others, the following protocol should be followed, and documented on an Incident Report.

Beck Depression Inventory-II (BDI) Question 9

→ In the past few days, subject selects answer #1, 2, or 3 (I have thoughts of killing myself, but I would not carry them out, I would like to kill myself, or I would kill myself if I had the chance).

When assessments are completed over the phone or online during regular business hours the following protocol will be completed within 24 hours.

PROTOCOL TITLE: The Mothers and Babies Text Project

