Within 24 hours of the study participant's completion of their assessments a member of the Research team will call the study participant and will let the participant know that he/she will be contacting their home visiting program to let them know about the difficulties they are having with thoughts about death/suicide/hurting yourself/others, so they can reach out and offer support. The research team member will ask the study participant the following questions:

- "Are you thinking about killing yourself?"
- "Have you ever tried to hurt yourself before?"
- "Have you thought of ways that you might hurt yourself?"
- "Do you have pills/weapons in the house?"
- "Do you think you might try to hurt yourself today?"

- *If her response is Yes, then call 911 and stay on the phone with her until help arrives*

All individuals that complete the above surveys will receive the following resources immediately upon answering the above answer choices on the noted assessments

- ✓ Home Visiting Program Office phone number
- ✓ National Suicide Prevention Hotline (24/7)
 - [name] ([name])
 - <http://www.suicidepreventionlifeline.org/> (online chat available 24/7: "Lifeline Chat")
- ✓ Postpartum Support International (outside of Illinois)
 - [name]
- ✓ NorthShore Perinatal Support, 24-hour Crisis Hotline (in Illinois)
 - [name] [contact])

All of these resources (except the home visiting program office number) will also be shared with all study participants, regardless of answers to assessment questions, at the end of each assessment. The research team member will stay on the phone with those individuals who endorse the possibility of imminent self-harm. After the research team member ends the call with the study participant, they will call the Program Manager with relevant details, reporting what the client said and endorsed, as well as the information they gathered during the assessment and call with the participant. The research team member will then follow up with an email to the home visitor, supervisor, Project Manager, as well as the PI with relevant details.

If the survey is completed outside of regular business hours (i.e. weekends/holidays) the research team will follow-up with the participant within 24 hours. As noted above, the risk would be acknowledged in real time as the participant would still receive resources immediately following their answer selection to the above survey questions.

Text Message Responses:

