REDCap will be programmed to notify the Research Manager if a participant indicates self-harm on a survey response. In addition, the Research Manager will review all text message responses no later than 24 hours from the time the text message response is sent. If a participant indicates self-harm on a survey response or a response to a text message, they will automatically receive resource messages listed above. In addition, the Research Manager will contact the participant's Program Manager to notify them of their client's response within this 24 hour period. HV programs have their own safety protocols they will follow. HV Program Managers are typically licensed clinical social workers who have the necessary skills to assess the extent to which clients need further response to their mental health needs. Moreover, they have established relationships with their clients. If a text message is received outside of regular business hours (i.e. weekends/holidays) the research team will follow-up with the participant's Program Manager within 24 hours. As noted above, the risk would be acknowledged in real time as the participant would still receive resources immediately following their answer selection to the above survey questions.

We believe this to be a reasonable expectation in regards to protecting human subjects and the role of the research team. Previous Mothers and Babies studies conducted by the PI, as well as other nationally representative studies of perinatal women have shown that less than 1% of study participants will endorse the most “severe” response choice on survey items related to suicidality. As such, we anticipate that the number of study participants who endorse the most severe response related to suicidality outside of regular business hours over the course of this study will likely be < 1 individuals. As such, we believe our approach to handling this potential risk to study participants—i.e., immediate provision of 24/7 resources and follow-up by the study team no later than 24 hours—is reasonable given its likelihood of occurrence. Moreover, women receiving the Mothers and Babies intervention (100% of the sample) will be receiving information on modifying harmful thought patterns that may contribute to decreased thoughts about self-harm.

16.0 Data and if applicable, Specimen Banking:

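### For the 36 Phase 2 male partners, the only active referral the study makes short of 911 is to the home visiting program, whose enrolled client is the woman

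*Combined protocol and SAP*

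**What the plan says.** Section 15.0 (Online Survey) sets out two survey responses.

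- **Self-harm.** "Any study participant who endorses thoughts of self-harm will be referred to the supervisor at the home visiting program, by the Project Manager". The supervisor then judges danger and next steps under the agency's own protocol, and the principal investigator is told. BDI item 9, answers 1 to 3, triggers a research-team call within 24 hours, with 911 if the participant may act that day. The caller then telephones the Program Manager and is to "follow up with an email to the home visitor, supervisor, Project Manager, as well as the PI with relevant details".
- **Severe depressive symptoms.** "should administration of depression scale indicate the participant is experiencing severe depressive symptoms, the supervisor at the home visiting program will be notified", so that the supervisor can arrange treatment referrals for a person described as the supervisor's client.

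Section 10.0 follows the same path for suicidal ideation on an assessment. The study is to "refer the study participant to a licensed clinical social worker at each HV program (typically the program manager") and to give crisis hotline details. It adds: "Non-imminent concerns will be flagged and discussed in weekly team meetings and shared with providers as necessary".

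Section 4.0 gives all Phase 2 measures, including the BDI-II in Table 2, to both sexes. Section 3.0 requires the woman to be enrolled in home visiting. The man need only be an English-speaking adult and her partner. When Section 10.0 assures participants that declining a question will not harm their standing with the program, the relationship it protects for men is "their partner's relationship with their HV program (male clients").

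**The concern.** The safety procedure appears to have been written for the home visiting client and then applied to her partner. Its pronouns are female. Two of the reasons Section 15.0 gives for the approach being adequate do not clearly describe the men. One is about Program Managers: "Moreover, they have established relationships with their clients". The other relies on "women receiving the Mothers and Babies intervention (100% of the sample"), whereas the men receive Fathers and Babies (FAB).

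At stake is treatment linkage for a man in difficulty who is not a 911 case. His own contact with the program may be slight. Section 4.0 lets the Project Manager deliver his first session by phone, and makes later sessions with him optional. If his follow-up surveys fall 3 and 6 months after the intervention, as one sentence in Section 4.0 has it, two of his three BDI-II assessments come after his texts have ended. The study will then hold clinical information about him, while the only referral it makes itself goes to an agency tied to him through his partner.

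**Working it through.** The plan states no figure on this point, so the check is mainly a comparison of sections.

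**1. Is the man himself a home visiting enrollee?** Sections 3.0 and 4.0 require enrollment of the woman and partnership of the man. Section 10.0 describes the program tie as his partner's. One garbled sentence in Section 8.0 could be read as putting the men in home visiting, but the other sections settle it: enrollment is not a condition for men.

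**2. Does he meet the triggers?** Yes. He completes the BDI-II, and the self-harm rule covers any study participant.

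**3. What follows each trigger?**

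| Step | Item 9 endorsed | Severe score, item 9 not endorsed |
|---|---|---|
| Hotline list | Immediately, and again at the end of the survey | At the end of the survey, as for everyone |
| Research-team call within 24 hours | Yes | Not provided in Section 15.0 |
| 911 | If he may act that day | Not applicable |
| Notice to the principal investigator | Yes | Not stated |
| Notice or referral to the home visiting program | Yes | Yes |
| Weekly review, sharing with unspecified providers (Section 10.0) | If not imminent | Possible |
| Direct referral by the study to another clinician or service | None stated | None stated |

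The last row is the gap in both columns. In the right-hand column, notice to the supervisor is the only step in Section 15.0 that the score itself triggers.

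**4. Automated advice.** The text-message part of Section 15.0 includes a message telling the person to go to a hospital or call a doctor. A later paragraph sends survey respondents who indicate self-harm the resource messages listed above, which may mean this message or the earlier hotline list. On either reading he must act on it himself, and it is not triggered by a severe score without self-harm.

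**5. Scale.**

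- Share of Phase 2 respondents: 36 / (36 + 36) = 36/72 = 50%.
- Section 2.0 gives depression in fathers as 5-10% in one place: 36 × 0.05 = 1.8 and 36 × 0.10 = 3.6 men. In another place it gives 5-7% for new fathers: 1.8 to 36 × 0.07 = 2.5 men.
- Chance of at least one depressed man, assuming independence: 1 − 0.95^36 = 84%; 1 − 0.93^36 = 93%; 1 − 0.90^36 = 98%.

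These figures describe depression of any severity and are context only. The documents give no rate of severe scores or of item 9 endorsement in men. The figure of under 1% in Section 15.0 concerns only the most severe answer on suicidality items, and the outside studies it cites are of perinatal women.

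**The case against.** The case on the other side has real weight.

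- **The men are covered.** The rule says any study participant. An item 9 response brings immediate resources, a call within 24 hours, notice to the principal investigator and the program, and 911 if needed. A reader might infer that men have no safety response; the documents show otherwise.
- **The program knows them.** Section 4.0 calls the men clients, has home visitors send their 51 texts, and lets home visitors deliver their first session. The referral wording about the supervisor's client can therefore include them. This stands. It shows that the program can act for a man, but it does not add a second route.
- **Other help is mentioned.** The hospital-or-doctor message may reach survey respondents, and one hotline points to community resources. It would therefore be wrong to say that nothing but the program is ever named. What remains is that the study itself makes no other referral.
- **Much is unseen.** Agency protocols, the referral form, the consent pages and the 14 male baseline items are not in the file. A reader might infer that a program would refuse a man, or that no provider or emergency contact is held for him. Neither can be concluded.
- **He can be traced.** Section 7.0 records phone numbers and addresses for women and their partners, and Section 4.0 provides for check-ins to keep contact details current. A claim that the study would have no means of reaching him would be overstated.
- **Women have no named outside provider either.** True, but they are the agency's enrolled clients, which is what the single route assumes.

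The e-mail to the partner's home visitor might be read as a confidentiality breach. Section 10.0 makes non-disclosure the default with an exception for risk of harm, and Section 15.0 confines the message to relevant details. It is a point for tightening and does not carry the concern.

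**Conclusion.** The concern holds in a narrow form. Short of 911, every referral the study itself makes for a Phase 2 man goes to the home visiting program, and his eligibility does not make him an enrolled client of it. The sharpest case is a severe BDI-II score without item 9. There, Section 15.0 provides notice to the supervisor and no study-team call. Beyond that are only the hotline list that everyone receives and the unspecified sharing with providers in Section 10.0.

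The arrangement applies to all 36 men, half of the Phase 2 respondents. How many would trigger it is unknown. The 84-98% range should not be read as the chance that the gap is met, since it is the chance of at least one depressed man of any severity. The conclusion rests on the text supplied, and unseen agency protocols or baseline items could narrow it. The two justifications in Section 15.0 that do not clearly fit the men are drafting matters. This is a low-cost safety improvement that should be made; it does not affect the outcomes or the analysis.

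**What to change.** 1. At baseline, ask each man for his own health care provider and an emergency contact of his choice, unless the unseen items already do so.
2. Have the research team call any man who scores in the severe range or endorses item 9 (answers 1 to 3). The second call already exists. On the call, refer him directly to his own provider or a community mental health service, and use the emergency contact if he cannot be reached.
3. Keep the notices to the principal investigator and the program as now planned; the direct referral is an addition.
4. Limit what is sent to his partner's home visitor to what safety requires.
5. While amending Section 15.0, reword its justification so that it also covers men receiving FAB.

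The cost is a few baseline items, one IRB modification, slightly longer item 9 calls and an extra call for each man who scores severe without item 9. It needs no new staff and no change to outcomes or sample size.

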that prompt discussion about the following topics: (1) satisfaction with the existing FAB Course, identifying the most and least enjoyable, understandable, and useful content; (2) effectiveness of content delivery (e.g., web-based links to content, text-messages); (3) additional topics that should be included to meet the needs of new fathers and families; and, (4) methods to best engage fathers in the FAB intervention. Focus groups and key informant interviews will be audio-recorded, transcribed, and then analyzed to identify common themes to guide FAB Course revisions. In keeping with a collaborative approach that our research team has undertaken throughout our MB and FAB work, during our focus group and key informant interviews we will identify 2-3 fathers from different cultural backgrounds to serve as consultants, who will remain engaged in an iterative process of review and feedback about FAB revisions.
